STATISTICAL ANALYSIS PLAN

NCT03223883

August 19, 2024

Statistical considerations and power calculation

BA-FMD is the primary outcome of this randomized controlled trial. The change in BA-FMD from baseline to 12 months after randomization will be compared between the curcumin and placebo groups. Other secondary outcomes include aPWV, systemic and endothelial markers of inflammation and oxidative stress, and cognitive function measured by the NIH Cognition Toolbox Battery. Power and sample size calculation ¹⁻³ is based on two-sample t-test of change in FMD by using PASS⁴. Preliminary data provides estimate of the mean and standard deviation (SD) of BA-FMD change as 1.25 and 0.88 under curcumin (n=17) and 0.08 and 0.40 under placebo (n=13), respectively. This provides a large between-conditions difference (i.e. 1.25 - 0.08 = 1.13) and effect of 1.7 taking account heterogeneity. Given the sample mean of 0.08 under control condition of usual care in Van Craenenbroeck, et al.⁵, we have assumed 0.10 as mean change in BA-FMD under placebo conditions. While there is no published literature to estimate the mean change in BA-FMD under curcumin in CKD, we believe it should be smaller than 1.25; in other words, the between conditions difference should be smaller than 1.13. Based on Van Craenenbroeck, et al. ⁵ and Thambyrajah, et al. ⁶ where the betweenconditions difference was 0.33 and 0.80, respectively, we assumed a difference of 0.6 between curcumin and placebo, considering difference between studies in intervention, study population, duration of study, and the observed difference in preliminary data. In summary we have the following assumptions: mean and SD of FMD change from baseline to 12 months after randomization are 0.70 and 0.90 under curcumin and 0.10 and 0.40 under placebo, respectively. With target power of 95% and 2-sided alpha 0.05, calculation by PASS indicates a sample size of 37 patients per group. We are going to enroll a total of 88 patients assuming approximately 18% potential loss to follow-up and equal randomization to the curcumin and placebo groups with 44 participants in each group. Power for cognitive function and other secondary outcomes: Based on the preliminary data from our pilot study of 12 weeks treatment (curcumin vs. placebo) with small sample size (17 patients per group), improved cognitive function was observed in the curcumin group but not in placebo. The effect size for episodic memory can be estimated as 0.8 for both picture sequence memory (data showed 0.77) and fluid composite (data showed 0.83). This implies that 37 patients per group will provide more than 90% power, based on calculation by PASS, with 2-sided significant level of 0.05 by using the two-sample t-test. Similarly, for other secondary outcomes, including change in aPWV and systemic and endothelial markers of inflammation and oxidative stress, 37 patients per group will provide more than 90% power if the effect size is 0.8 or larger. The power will be at least 95% if 44 patients per group can be included and effect size is 0.8.

Statistical analysis

Descriptive statistics will be provided for demographic characteristics, baseline measure, and outcome variables as appropriate. For example, mean and SD will be provided for continuous variables and proportion for categorical variables. 95% confidence intervals will also be provided if appropriate. We don't anticipate necessary data transformation but will confirm it before analysis.

All outcome analyses will be based on the "intent-to-treat (ITT)" principle. For Aim 1a, change in BA-FMD from baseline to 12 months after randomization will be compared between curcumin and placebo groups by using two-sample t-test. The same analysis will be performed for aPWV. As an additiaonI analysis, repeated measures analysis will be employed to compare the two groups in the change in both BA-FMD and aPWV from baseline to month 6 and 12, and the compound symmetry covariance structure will be specified. Treatment group indicator, time, and their interaction will be included as fixed effects in the model. We will explore the impact of sex, race, baseline CKD stage, and physical activity by including them as covariates in a regression model. Of note, we are stratifying by age and DM status (as noted above). For Aim 1b, repeated measures analysis will be performed for change in both BA-FMD and aPWV before and after vitamin C infusion at all three time points, the same analysis as the previous one in Aim 1a except that we now have three time points and that other covariance structures will also be explored. In addition, correlation analysis will be performed to examine the association between change in vascular function (BA-FMD and aPWV) and change in levels of inflammatory and oxidant markers including systemic measures (high-sensitivity CRP, IL-6, MCP-1, and oxLDL) and endothelial measures (eNOS and eNOS phosphorylated at Ser 1177, NF-κB, NAD(P)H oxidase,

and nitrotyrosine). Finally, repeated measures analysis will be employed to compare between groups the change in inflammatory and oxidant markers from baseline to month 6 and 12. For Aim 2, the same analysis as in Aim 1a will be performed to evaluate the treatment efficacy on cognitive function, including correlation analysis to examine the association between change in vascular function (BA-FMD and aPWV) and cognitive function. Based on our pilot study, we don't anticipate severe adverse events but we will tabulate all observed events. Data of pill count will be summarized and analyzed as appropriate. All analyses will be performed by using SAS 9.4, SAS Institute Inc., Cary, NC, USA⁷.

Loss to follow-up and missing data: We anticipate loss to follow-up and missing values will occur, but based on our experience and track record we do not anticipate large number of loss to follow-up. We thus plan to derive conclusions based on complete case analysis by using two-sample t-test of the outcome variables. We will tabulate baseline characteristics to examine any difference between those lost to follow up and those complete the study. In the unlikely event of >10% missing data, we will perform multiple imputation under assumption of missing at random (MAR) mechanism ⁸ and examine any change in conclusions.

References

1. Julious SA. Sample Sizes for Clinical Trials. Second Edition ed. Boca Raton, FL: Chapman and Hall/CRC; 2010.

3. Zar JH. Biostatistical analysis. Second Edition ed. Englewood Cliffs, New Jersey: Prentice- Hall; 1984.

4. PASS 14 Power Analysis and Sample Size Software. NCSS, LLC., 2015. at ncss.com/software/pass.)

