- **Experimental Design:** 88 subjects, recruited at the University of Iowa Hospitals and Clinics (UIHC) and The Iowa City VA Medical Center, will be randomized to receive either placebo or curcumin (2000 mg/ day) for 12 months and stratified randomization will be employed based on age \geq 55 yeas ⁸⁻¹⁰ and baseline DM status ¹¹. Block randomization is an alternative for consideration. Study outcomes will be evaluated at baseline, 6 months, and 12 months (except cognitive function will be evaluated at baseline and 12 months only).

- **Curcumin supplementation:** Based on our preliminary data we will use a solid lipid curcumin particle (SLCP, Longvida, Verdure Sciences) at a dose of 2000 mg/d. Based on our preliminary data, we believe this will be an effective dose to improve vascular function in patients with CKD. Longvida will provide the supplement in addition to identical-looking placebo. The randomization table will be generated by [name] and provided to Longvida. Once a subject is randomized, Longvida will package and ship the study drug (curcumin or placebo). The package will only state "study drug" in order to guarantee blinding of all the study staff and participants. As we show in the **Preliminary Data** and **Protection of Human Subjects** sections, curcumin was well-tolerated with a small number of adverse events (mainly gastrointestinal discomfort).

- **Rational for the duration of the study:** In specific aim 2, we intend to evaluate whether curcumin improves cognitive function in patients with CKD. Although our preliminary data suggests that curcumin may improve cognition in as little as 12 weeks, we believe a longer duration is necessary to minimize practice effects from repeated cognitive testing ^{12,13}. Thus, the study duration will be 12 months. In addition, this longer duration will

enhance our ability to detect a benefit on vascular stiffness (specific aim 1). Large elastic artery stiffness reflects structural changes of the extracellular matrix in the vessel wall ¹⁴. Based on this, the longer duration of study will allow the treatment to reverse these structural changes in the vasculature. The vascular measurements will be conducted at baseline, 6 months, and 12 months. In order to reduce practice effects, cognitive function will be measured at baseline and 12 months only.

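### The primary BA-FMD analysis is an unadjusted t-test on change that omits baseline and the planned stratification factors: valid, but possibly less precise than the collected data allow

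*SAP*

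**What the plan says.** For Aim 1a (SAP, Statistical analysis), "change in BA-FMD from baseline to 12 months after randomization will be compared between curcumin and placebo groups by using two-sample t-test". The SAP applies the same analysis to aPWV and extends it to cognition: "For Aim 2, the same analysis as in Aim 1a will be performed to evaluate the treatment efficacy on cognitive function". The paragraph on loss to follow-up confirms that this test decides the trial: "We thus plan to derive conclusions based on complete case analysis by using two-sample t-test of the outcome variables".

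Two further models are described:

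- The additional repeated-measures analysis has treatment, time and their interaction as its only fixed effects.
- The exploratory regression is described as follows: "We will explore the impact of sex, race, baseline CKD stage, and physical activity by including them as covariates in a regression model". The next sentence remarks that age and DM status are stratified on, but it places neither in a model.

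In the Protocol, under Experimental Design, "stratified randomization will be employed based on age" (55 or older) and baseline DM status. The following sentence leaves the method partly open: "Block randomization is an alternative for consideration".

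The sample size (SAP, Statistical considerations and power calculation) is based on the same two-sample t-test on change. On the effect, it says of two published trials that the between-conditions "difference was 0.33 and 0.80, respectively, we assumed a difference of 0.6 between curcumin and placebo".

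**The concern.** Analysing change is the same as adjusting for baseline with the slope set to 1. When the true slope of the 12-month value on baseline is below 1, which is usual when a measurement has appreciable within-person variability, subtracting the whole baseline adds noise. ANCOVA estimates the slope and removes that noise.

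Allocation that is balanced within age and DM strata also reduces the true sampling variance of the treatment difference if those factors predict outcome. A test that ignores the strata does not credit that reduction, so its standard error is too large. The SAP proposes to explore four covariates that were not stratified on and leaves out the two that were.

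At stake is the width of the confidence intervals for BA-FMD, aPWV and the cognitive scores, and the chance of detecting an effect smaller than the one planned for.

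**Working it through.** **Inputs from the SAP.** SD of change 0.90 (curcumin) and 0.40 (placebo); difference 0.6; two-sided alpha 0.05; target power 95%; 37 per group.

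**Inputs not in the documents.** The baseline SD of BA-FMD, its correlation r with the 12-month value, and how strongly age and DM predict outcome. Ranges are used for the first two.

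**1. The plan's own figure.**
- Mean change variance: (0.90² + 0.40²)/2 = (0.81 + 0.16)/2 = 0.485, so the root-mean-square SD is 0.696.
- Standard error at 37 per arm: √(0.97/37) = 0.162. Welch degrees of freedom: 49.7.
- Noncentral-t power at a difference of 0.6 is 95.3%, and 37 is the smallest n reaching 95%. The stated sample size reproduces.

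**2. Gain from estimating the baseline slope.** Suppose baseline and 12-month variances are equal (σ²) and the slope is common to both arms. Then the change score has variance 2σ²(1 − r) and ANCOVA has residual variance σ²(1 − r²). The ratio is (1 − r²)/[2(1 − r)] = (1 + r)/2.

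Setting 2σ²(1 − r) = 0.485 gives the baseline SD that each r implies: σ = √(0.485/[2(1 − r)]). Power below is at 37 per arm, with both arm variances multiplied by (1 + r)/2.

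| r (assumed) | Implied baseline SD | Variance ratio | Power, difference 0.6 | Power, 0.4 | Power, 0.33 |
|---|---|---|---|---|---|
| Planned t-test | – | 1 | 95.3% | 67.8% | 51.5% |
| 0.5 | 0.70 | 0.75 | 98.7% | 79.9% | 63.6% |
| 0.7 | 0.90 | 0.85 | 97.6% | 74.8% | 58.2% |
| 0.8 | 1.10 | 0.90 | 96.9% | 72.4% | 55.8% |
| 0.9 | 1.56 | 0.95 | 96.1% | 70.0% | 53.6% |
| 0.95 | 2.20 | 0.975 | 95.7% | 68.9% | 52.6% |

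As r approaches 1 the gain vanishes and power returns to the first row.

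**3. Allowing for the unequal arm SDs.** One r for both arms is a simplification. With equal variances over time, each arm's correlation is 1 − s²/(2σ²), where s is that arm's SD of change. At σ = 0.70 this gives 1 − 0.81/0.98 = 0.17 under curcumin and 1 − 0.16/0.98 = 0.84 under placebo. At σ = 1.5 it gives 0.82 and 0.96.

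A simulation with these arm-specific correlations and a common-slope ANCOVA (60,000 trials per setting) gave variance ratios, ANCOVA to change score, of 0.760, 0.863, 0.913, 0.961, 0.985 and 1.00 at baseline SDs of 0.7, 0.9, 1.1, 1.5, 2.0 and 3.0. The formula therefore survives the unequal SDs, and the saving runs from 24% to nothing.

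**4. Validity of the planned test.** Simulated trials with no treatment effect (74 patients, four strata, blocks of four, 10,000 runs per setting, r from 0.3 to 0.7) showed no bias. The t-test's type I error was 0.049 to 0.052 when the strata did not affect outcome. It was 0.028 to 0.043 under the strata effect assumed in the simulation. The test is conservative there, not inflated.

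**The case against.** The strongest reply is that nothing here is an error. The test is valid, the trial was sized on it, and 37 per group gives the stated power. That is correct, and the point is put as one of efficiency only.

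Second, the gain may be zero. The documents favour no particular baseline SD, and the top of the range needs very different correlations in the two arms (0.17 and 0.84). This also stands: the lower end of every power range is the unadjusted figure.

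Third, the extra terms could cost precision. With two non-predictive covariates not balanced by design, simulated ratios for the full model were 0.99, 1.01 and 1.03 at baseline SDs of 1.5, 2.0 and 3.0. When the strata are balanced by the randomisation, as planned, the two terms cost essentially nothing, so this objection falls away if stratification was used.

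Fourth, the 0.33 comes from an exercise-training trial, and the SAP weighed it with other evidence before choosing 0.6. At 0.33, even the best case reaches only 63.6%. That is so: adjustment would not rescue the trial at that effect, but it would narrow the interval if r is moderate.

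Finally, the remark about stratifying can be read as saying that age and DM are dealt with by design. Balance by design does not correct the standard error; the analysis must include the factors for that.

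**Conclusion.** The concern holds as a loss of precision, not of validity. Estimating the baseline slope would reduce the variance of the BA-FMD difference by between about a quarter and nothing, depending on a baseline SD the documents do not give and on equal variances at baseline and 12 months. At the planned difference of 0.6 the gain in power is at most about 3 percentage points (95.3% to 98.7%). At 0.4 or 0.33 it is at most about 12 points.

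Any gain from age and DM comes on top and cannot be sized from the documents; it also depends on the stratification having been carried out. For aPWV and cognition the same reasoning applies, but the SAP gives no SDs from which to size it. The change is worth making because it uses data already collected.

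**What to change.** In a dated SAP amendment made before unblinding:

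- Name as primary an ANCOVA of 12-month BA-FMD (or its change, which gives the same treatment estimate) on treatment, baseline BA-FMD and the stratification factors actually used. These are age group and DM, once it is confirmed that the block-randomisation alternative in the Protocol did not replace them.
- Specify a variance estimate that allows the arms to differ, since the SAP plans on SDs of 0.90 and 0.40.
- Use the same form for aPWV and the NIH Toolbox scores, each with its own baseline.
- Keep the unadjusted t-test as a supportive analysis.

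The cost is SAP wording only: baseline BA-FMD, age and DM status are already collected, and no patients or procedures are added. The documents do not state the blinding status. If treatment codes have already been opened, replacing the primary test would be a post hoc change, and the ANCOVA should then be reported as supportive.

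### The Aim 1b vitamin C model treats the pre-treatment visit as an outcome time, so its month-12 contrast is an unadjusted change score: unbiased, but less precise than the collected data allow

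*SAP*

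**What the plan says.** The SAP section on statistical analysis describes two repeated-measures analyses that share one model.

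- **Aim 1a, additional analysis.** The outcome is "change in both BA-FMD and aPWV from baseline to month 6 and 12", so both modelled times follow the start of treatment. On the model terms the SAP says: "Treatment group indicator, time, and their interaction will be included as fixed effects in the model". The covariance is compound symmetry.
- **Aim 1b.** The outcome is "change in both BA-FMD and aPWV before and after vitamin C infusion at all three time points". The model is "the same analysis as the previous one in Aim 1a except that we now have three time points", and further covariance structures are to be tried.

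The protocol's experimental design gives the three times as baseline, month 6 and month 12. Its session list places the vitamin C infusion in Session 2, the baseline session, and starts study drug after that session. The first of the three Aim 1b times is therefore before treatment.

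For Aim 1b the SAP enters no baseline covariate, sets no common baseline mean for the two arms, and does not say which term or contrast answers the aim.

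**The concern.** In Aim 1a the baseline has already been subtracted, so every modelled time is a post-treatment time. In Aim 1b the same fixed effects are carried over to a set of times that includes baseline, and each arm has its own free mean there. Randomisation implies that the two arms share one expected baseline response, and the model makes no use of that.

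The contrast that measures the treatment effect is then the arm difference at month 12 minus the arm difference at baseline. The vitamin C response is itself a difference between two vascular measurements, so it may well vary considerably from visit to visit. If it does, subtracting the whole baseline value adds noise that a covariate adjustment would avoid. At stake is the precision of the estimated effect of curcumin on oxidative-stress modulation, a mechanistic secondary aim.

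**Working it through.** **1. The plan's own figures.** The SAP gives no power or sample-size figure for the vitamin C analysis, so I checked the nearest ones.

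- Primary outcome: the means and SDs of change "are 0.70 and 0.90 under curcumin and 0.10 and 0.40 under placebo", a difference of 0.60. The SAP states: "With target power of 95% and 2-sided alpha 0.05, calculation by PASS indicates a sample size of 37 patients per group". The unequal-variance t-test gives power 0.948 at 36 and 0.953 at 37 per group, so 37 reproduces.
- Secondary outcomes: "37 patients per group will provide more than 90% power if the effect size is 0.8 or larger". The two-sample t-test (noncentral t, two-sided 0.05) gives 92.4% at 37 per group. This reproduces too.

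**2. Inputs for Aim 1b.**

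- 37 per arm: the SAP's evaluable number.
- Effect of 0.8 SD on the change scale: assumed. The SAP uses 0.8 for other secondary outcomes and does not state it for the vitamin C response.
- Between-visit correlation ρ: assumed, 0.3 to 0.9. The documents give none.
- Equal variance at each visit (set to 1) and the same ρ between visits: assumed.

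**3. Variance of the month-12 contrast, per participant.**

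- Change score: 2(1 − ρ).
- Baseline-adjusted: 1 − ρ².
- Ratio, adjusted to unadjusted: (1 − ρ²) / [2(1 − ρ)] = (1 + ρ)/2.

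Adjustment divides the standardised effect's denominator by a smaller SD, so 0.8 becomes 0.8/√[(1 + ρ)/2].

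| ρ (assumed) | 2(1 − ρ) | 1 − ρ² | Variance cut | Standardised effect after adjustment | Power, change score | Power, adjusted |
|---|---|---|---|---|---|---|
| 0.3 | 1.40 | 0.91 | 35% | 0.992 | 92.4% | 98.8% |
| 0.5 | 1.00 | 0.75 | 25% | 0.924 | 92.4% | 97.5% |
| 0.7 | 0.60 | 0.51 | 15% | 0.868 | 92.4% | 95.7% |
| 0.9 | 0.20 | 0.19 | 5% | 0.821 | 92.4% | 93.6% |

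**4. Simulation check.** With 10,000 runs, ρ = 0.5, 37 per arm and a true effect of 0.65 (in SDs of a single visit) at months 6 and 12, the month-12 change contrast averaged 0.648, so it is unbiased. Its variance was 1.31 times that of the baseline-adjusted estimate (theory: 1/0.75 = 1.33). In one simulated data set, a mixed model with group, time and interaction gave a month-12 interaction coefficient of 0.472, equal to the simple difference in mean change.

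**5. The visit-averaged group term, for comparison.** If the true arm differences at baseline, month 6 and month 12 are (0, d, d), their average is 2d/3. If they are (0, 0, d), it is d/3. In the simulation above it averaged 0.431, about 2/3 of 0.65.

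**The case against.** **A stronger reading: the Aim 1b treatment effect is diluted.** A reader might infer this because the group main effect averages over an untreated visit. The documents do not support it. The interaction is in the model, its contrasts are not diluted, and the Aim 1a analysis being copied compares the groups on change, which points to the interaction. Under reference-cell coding the printed group coefficient is the difference at one visit and not the average. Dilution to 2/3 or 1/3 would follow only if the visit-averaged term were reported as the treatment effect, and the SAP does not say that it will be.

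**A second stronger reading: the baseline value is thrown away.** It is not. It is subtracted, which is valid; the loss is one of efficiency.

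**Further objections that stand in part.**

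- The size rests on assumptions. At ρ = 0.9 the gain is 5% in variance and about one point of power.
- At the assumed effect of 0.8 the unadjusted contrast keeps 92.4% power, above the 90% that the SAP claims for secondary outcomes. It is not underpowered on those inputs.
- Unadjusted change scores are also used for the primary BA-FMD comparison, for aPWV and for cognition, so the efficiency argument is not peculiar to Aim 1b. What is specific here is that the baseline visit sits among the outcome times with free arm means.
- The SAP already allows covariance structures other than compound symmetry for Aim 1b. Asking for unstructured in particular is a preference; asking for one structure chosen in advance is not.

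None of this removes the point that a more precise analysis can be had from data the trial already collects.

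**Conclusion.** The concern holds as a loss of precision, not as a bias. The Aim 1b month-12 contrast is a valid but unadjusted change score. Baseline adjustment multiplies its variance by (1 + ρ)/2, a cut of 35% at ρ = 0.3 falling to 5% at ρ = 0.9. With an effect of 0.8 SD of change and 37 per arm, that is a gain of 6.4 percentage points of power at ρ = 0.3 (98.8 − 92.4) and 1.2 at ρ = 0.9 (93.6 − 92.4).

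These sizes depend on equal variances, on an assumed ρ and on an assumed effect for this outcome; the direction does not change for any ρ below 1. A low ρ is plausible for a difference-type measure, but the documents do not settle it. The result concerns a mechanistic secondary aim only.

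**What to change.** Amend the Aim 1b paragraph of the SAP in three respects.

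1. **Use of baseline.** Either model the month 6 and month 12 vitamin C responses with the baseline response as covariate (its coefficient allowed to differ by visit), or keep all three visits and constrain the two arms to a common baseline mean.
2. **Test.** Name the arm difference at month 12 as the Aim 1b test. This also removes any chance that the visit-averaged group term is reported as the treatment effect.
3. **Covariance.** Fix one structure in advance, for example unstructured, in place of an open exploration.

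The cost is a few sentences in the SAP and a few lines of SAS. No visit, measurement or sample-size change is needed.

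### The vascular-marker and vascular-cognition correlations name no treatment-arm term, so as written they mix a shared drug effect with any patient-level association (minor, supportive analyses)

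*SAP*

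**What the plan says.** In the SAP's Statistical analysis section, Aim 1b includes this step: "correlation analysis will be performed to examine the association between change in vascular function (BA-FMD and aPWV) and change in levels" of four systemic markers (high-sensitivity CRP, IL-6, MCP-1, oxLDL) and five endothelial ones (eNOS, phosphorylated eNOS, NF-κB, NAD(P)H oxidase, nitrotyrosine). With two vascular measures that makes 2 × 9 = 18 pairs. Aim 2 repeats the Aim 1a analysis for cognition, "including correlation analysis to examine the association between change in vascular function (BA-FMD and aPWV) and cognitive function".

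No coefficient, partial correlation or within-arm analysis is named for either set. Arm is named for the repeated measures model of Aim 1a: "Treatment group indicator, time, and their interaction will be included as fixed effects in the model". The exploratory covariates leave it out and are not tied to the correlations: "We will explore the impact of sex, race, baseline CKD stage, and physical activity by including them as covariates in a regression model". The protocol describes no correlation analysis.

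Randomised comparisons of the same variables are already planned. BA-FMD, aPWV and cognition are compared by arm, and for the markers "repeated measures analysis will be employed to compare between groups the change in inflammatory and oxidant markers from baseline to month 6 and 12".

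**The concern.** When a drug shifts two variables, the two arms form two separated clouds of points. A correlation fitted across both clouds picks up the distance between them, whether or not patients within a cloud show any association. This is not a type I error for the pooled correlation, whose true value really is non-zero. The difficulty is one of interpretation.

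The planned randomised comparisons already show whether curcumin moved each variable. What a correlation can add is whether patients with more marker or cognitive change also had more vascular change. If the drug moves both variables, the pooled coefficient cannot separate that from the shared drug effect. A significant result could then be read as a patient-level link when it only restates the two treatment effects.

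**Working it through.** **Inputs from the SAP power section.** BA-FMD change: mean 0.70 (SD 0.90) on curcumin, 0.10 (SD 0.40) on placebo; two-sided alpha 0.05; 37 per group after losses, 44 enrolled. Cognition: "The effect size for episodic memory can be estimated as 0.8 for both picture sequence memory" and the fluid composite (pilot values 0.77 and 0.83). For aPWV and the markers, 0.8 is only a condition: "37 patients per group will provide more than 90% power if the effect size is 0.8 or larger".

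**The plan's own figures.** Average SD = √((0.81 + 0.16)/2) = 0.696. The normal approximation gives n = 2(1.960 + 1.645)² × 0.485/0.36 = 35.01, so 36. The noncentral t gives 37 (power 95.3% Welch, 95.5% pooled), so the stated 37 reproduces. At effect size 0.8, power is 92.4% at 37 and 96.0% at 44, as the SAP says. It gives no power or target for the correlations.

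**Pooled correlation.** With 1:1 allocation, standardised drug effects d1 and d2, and pooled within-arm correlation r_w:

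r = (r_w + 0.25·d1·d2) / √[(1 + 0.25·d1²)(1 + 0.25·d2²)]

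Here d1 = 0.6/0.696 = 0.862. With d2 = 0.8 and r_w = 0:

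r = 0.1723 / √(1.1856 × 1.16) = 0.1723/1.1727 = 0.147

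Only the sign changes if the drug lowers one variable and raises the other. With r_w = 0.30 (assumption), r = (0.30 + 0.1723)/1.1727 = 0.40.

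**Chance of p<0.05.** Fisher approximation at N = 74: atanh(0.147) × √71 = 1.247, giving Φ(1.247 − 1.96) ≈ 0.24. At N = 88: 0.148 × √85 = 1.365, giving ≈ 0.28. Simulation (normal data, 200,000 trials per setting, zero within-arm correlation, equal SDs for the second variable) gives:

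| BA-FMD difference | d2 | Status of d2 | Pooled, 37/arm | Pooled, 44/arm |
|---|---|---|---|---|
| 0.6 | 0 | assumption | 5.1% | 5.0% |
| 0.6 | 0.3 | assumption | 8.0% | 8.5% |
| 0.6 | 0.5 | assumption | 13.0% | 14.5% |
| 0.6 | 0.77 | pilot, picture sequence memory | 23.1% | 26.6% |
| 0.6 | 0.8 | SAP rounded value | 24.5% | 28.1% |
| 0.6 | 0.83 | pilot, fluid composite | 25.5% | 29.8% |
| 0.33 | 0.8 | smaller BA-FMD difference | 11.2% | 12.6% |

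The arm-adjusted partial correlation rejects in 4.9% to 5.1% of trials in these settings. For equal-SD pairs such as aPWV with a marker, both effects are assumptions: at 37 per arm the pooled rate is 7.8% (0.5 and 0.5), 11.9% (0.8 and 0.5) and 21.7% (0.8 and 0.8).

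**Unequal SDs.** The SAP expects BA-FMD change to be more variable on curcumin. If the second variable is too (curcumin/placebo SD ratio k, an assumption), the arm-adjusted test is also somewhat liberal. Scale the second variable to average variance 1. For k = 2.25 its variances are 1.670 and 0.330. The variance of the cross-product is inflated by [(0.81 × 1.670 + 0.16 × 0.330)/2]/0.485 = 1.449. The true level is then 2Φ(−1.96/√1.449) = 10.3%. The same sum for k = 1.5 gives 8.0%. Simulation agrees: 8.0% to 10.3% arm-adjusted, against 26.3% to 28.3% pooled (d2 = 0.8, 37 per arm). Within-arm correlations combined by Fisher z stay at 5.0%; regression with arm and HC3 standard errors gives 5.2% to 5.6%.

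**Power at 37 per arm,** within-arm correlation 0.3 (assumption), no drug effect:

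| SDs | Pooled | Arm term | Fisher z | HC3 |
|---|---|---|---|---|
| Equal in both variables | 74.7% | 74.1% | 73.6% | 72% |
| SAP SDs for BA-FMD | 68.7% | 68.1% | 73.6% | 65–66% |
| SAP SDs, second variable k = 2.25 | 71.0% | 70.5% | 73.5% | 56% |

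With the planning drug effects added (0.6 and d2 = 0.8, SAP SDs), the pooled test rejects in 93.7% of trials and the arm-adjusted test in 68.0%. The surplus comes from the shared drug effect.

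**The case against.** **The SAP is silent; it does not say arm will be ignored.** True, and an analyst might adjust anyway. But the SAP names arm where it wants it, and an ordinary correlation is the plain reading. Aim 2's reference back to Aim 1a does not supply the term, because Aim 1a contains no correlation.

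**The stated purpose is only to examine an association, and a pooled one is a legitimate descriptive quantity.** Also true, and the SAP makes no mediation claim. That keeps the point minor. Even so, a pooled coefficient adds little to the randomised comparisons already planned.

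**The problem exists only if curcumin moves both variables.** Correct. If it moves one or neither, the pooled and adjusted tests behave almost alike. The SAP's planning values nevertheless anticipate movement in both for two cognition pairs.

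**The 24% rests on narrow support.** This stands as a limit on size. The SAP estimates both effects for only two of the pairs, and the cognition values come from a small 12-week pilot. For the 18 marker pairs and every aPWV pair, 0.8 is a conditional value.

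**The Aim 2 sentence does not clearly say change in cognition.** The wording is loose, but the Aim 1a analysis that it inherits is based on change, so the change-score reading is reasonable.

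**Robust methods go beyond what a minor point needs.** Fair: the SD ratios for the second variable are assumptions. That part should be optional.

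**Conclusion.** The concern holds as a minor, low-cost improvement to supportive analyses. It is certain that no arm term is specified for either set of correlations. The size is less certain. It is about 24% against 5% at 37 per arm where both planning effects are present, 8% to 13% for weaker assumed effects on the second variable, and nil where the drug moves only one variable. These rates assume normal data, 1:1 arms and no within-arm association. The near-exact 5% for the arm-adjusted test also assumes equal SDs in the second variable. Nothing here touches the primary comparison, its sample size or the other randomised comparisons.

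**What to change.** State in the SAP that the vascular-marker and vascular-cognition analyses will be partial correlations, or regressions of one change on the other, with treatment arm as a covariate, and that results will be described as associational. Say explicitly that the cognition variable is the change score.

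Optionally, because BA-FMD change is expected to be more variable on curcumin, also report within-arm correlations combined by Fisher z. Robust standard errors are an alternative. The Fisher z results above assume normal data and the same correlation in both arms.

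The cost is one sentence and one degree of freedom, with no new data. At the SAP's BA-FMD SDs and an assumed within-arm correlation of 0.3 without a drug effect, the arm term lowers power from 68.7% to 68.1% at 37 per arm and from 76.3% to 75.8% at 44. Fisher z costs no power in that setting; HC3 costs about 3 points, and more if both variables have strongly unequal SDs.
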